APPENDIX B: VARC-2 ENDPOINT DEFINITIONS

TABLE 1. Risk factors not captured by traditional risk scores

Comorbidities	Definition/criteria	Diagnostic modalities
Porcelain aorta or severely atherosclerotic aorta	Heavy circumferential calcification or severe atheromatous plaques of the entire ascending aorta extending to the arch such that aortic cross-clamping is not feasible	Noncontrast axial CT at levels: Sinotubular junction Tubular ascending aorta between the sinotubular junction and the innominate artery Innominate artery Entire transverse arch
Frailety	Slowness, weakness, exhaustion, wasting and malnutrition, poor endurance and inactivity, loss of independence Criteria: 5 m walking time* Grip strength* BMI <20 kg/m ² and/or weight loss 5 kg/year Serum albumin <3.5 g/dL Cognitive impairment or dementia	Medical history Physical examination Physical performance measures Cognitive assessments Laboratory tests
Severe liver disease/cirrhosis	Any of the following: Child-Pugh class C MELD score ≥10 Portal-caval, spleno-renal, or transjugular intrahepatic portal shunt Biopsy proven cirrhosis with portal hypertension or hepatocellular dysfunction	Medical history Physical examination Laboratory tests Child-Pugh classification MELD score Liver biopsy
Hostile chest	Any of the following or other reasons that make redo operation through sternotomy or right anterior thoracotomy prohibitively hazardous: Abnormal chest wall anatomy due to severe kyphoscoliosis or other skeletal abnormalities (including thoracoplasty, Potts' disease) Complications from prior surgery Evidence of severe radiation damage (eg, skin burns, bone destruction, muscle loss, lung fibrosis, or esophageal stricture) History of multiple recurrent pleural effusions causing internal adhesions	Medical history Physical examination Chest x-ray CT scan
IMA or other critical conduit(s) crossing midline and/or adherent to posterior table of sternum	A patent IMA graft that is adherent to the sternum such that injuring it during reoperation is likely. A patient may be considered at extreme risk if any of the following are present: The conduit(s) are radiographically indistinguishable from the posterior table of the sternum. The conduit(s) are radiographically distinguishable from the posterior table of the sternum but lie within 2–3 mm of the posterior table.	Axial CT scan images illustrating the graft crossing the midline so that the distance from sternum to graft can be measured. Angiogram from the lateral and PA projections and/or a CPR or VR (volume rendering) 3D reconstructed CT scan image showing relationships between the graft and the sternum
Severe pulmonary hypertension Severe right ventricular dysfunction	Primary or secondary pulmonary hypertension with PA systolic pressures greater than two-thirds of systemic pressure Criteria as defined by the guidelines (eg, TAPSE <15 mm, RV end-systolic area >20 cm ² , etc)†	Echocardiography, right and left-heart-catheterization documenting PA and systemic pressures Documentation of secondary causes of pulmonary hypertension

CT, Computed tomography; BMI, body mass index; MELD, Model for End-Stage Liver Disease; CPR, curved planar reformation; RV, right ventricular; IMA, internal mammary artery; PA, pulmonary artery; TAPSE, tricuspid annular plane systolic excursion. *Variable with respect to age and gender without validated scientific thresholds. †Rudski et al.⁷¹

TABLE 2. Mortality

All-cause mortality
Cardiovascular mortality
Any of the following criteria
Death due to proximate cardiac cause (eg, myocardial infarction, cardiac tamponade, worsening heart failure)
Death caused by noncoronary vascular conditions such as neurological events, pulmonary embolism, ruptured aortic aneurysm, dissecting aneurysm, or other vascular disease
All procedure-related deaths, including those related to a complication of the procedure or treatment for a complication of the procedure
All valve-related deaths including structural or nonstructural valve dysfunction or other valve-related adverse events
Sudden or unwitnessed death
Death of unknown cause
Noncardiovascular mortality
Any death in which the primary cause of death is clearly related to another condition (eg, trauma, cancer, suicide)

TABLE 3. Myocardial infarction

Periprocedural MI (≤ 72 h after the index procedure)
New ischemic symptoms (eg, chest pain or shortness of breath), or new ischemic signs (eg, ventricular arrhythmias, new or worsening heart failure, new ST-segment changes, hemodynamic instability, new pathological Q-waves in at least 2 contiguous leads, imaging evidence of new loss of viable myocardium or new wall motion abnormality) AND
Elevated cardiac biomarkers (preferable CK-MB) within 72 h after the index procedure, consisting of at least 1 sample postprocedure with a peak value exceeding $15\times$ as the upper reference limit for troponin or $5\times$ for CK-MB.* If cardiac biomarkers are increased at baseline (>99 th percentile), a further increase in at least 50% postprocedure is required AND the peak value must exceed the previously stated limit
Spontaneous MI (>72 h after the index procedure)
Any 1 of the following criteria:
Detection of rise and/or fall of cardiac biomarkers (preferably troponin) with at least 1 value above the 99th percentile URL, together with the evidence of myocardial ischemia with at least 1 of the following:
Symptoms of ischemia
ECG changes indicative of new ischemia [new ST-T changes or new left bundle branch block (LBBB)]
New pathological Q-waves in at least 2 contiguous leads
Imaging evidence of a new loss of viable myocardium or new wall motion abnormality
Sudden, unexpected cardiac death, involving cardiac arrest, often with symptoms suggestive of myocardial ischemia, and accompanied by presumably new ST elevation, or new LBBB, and/or evidence of fresh thrombus by coronary angiography and/or at autopsy, but death occurring before blood samples could be obtained, or at a time before the appearance of cardiac biomarkers in the blood.
Pathological findings of an acute myocardial infarction

*Previously in the original VARC it was $10\times$ and $5\times$ for troponin and CK-MB, respectively.

=

TABLE 4. Stroke and TIA

Diagnostic criteria
Acute episode of a focal or global neurological deficit with at least 1 of the following: change in the level of consciousness, hemiplegia, hemiparesis, numbness, or sensory loss affecting 1 side of the body, dysphasia or aphasia, hemianopia, amaurosis fugax, or other neurological signs or symptoms consistent with stroke
Stroke: duration of a focal or global neurological deficit ≥ 24 h; OR <24 h if available neuroimaging documents a new hemorrhage or infarct; OR the neurological deficit results in death
TIA: duration of a focal or global neurological deficit <24 h, any variable neuroimaging does not demonstrate a new hemorrhage or infarct
No other readily identifiable nonstroke cause for the clinical presentation (eg, brain tumor, trauma, infection, hypoglycemia, peripheral lesion, pharmacological influences), to be determined by or in conjunction with the designated neurologist*
Confirmation of the diagnosis by at least 1 of the following:
Neurologist or neurosurgical specialist
Neuroimaging procedure (CT scan or brain MRI), but stroke may be diagnosed on clinical grounds alone
Stroke classification
Ischemic: an acute episode of focal cerebral, spinal, or retinal dysfunction caused by infarction of the central nervous system tissue
Hemorrhagic: an acute episode of focal or global cerebral or spinal dysfunction caused by intraparenchymal, intraventricular, or subarachnoid hemorrhage
A stroke may be classified as undetermined if there is insufficient information to allow categorization as ischemic or hemorrhagic
Stroke definitions†
Disabling stroke: an mRS score of 2 or more at 90 days and an increase in at least 1 mRS category from an individual's prestroke baseline
Nondisabling stroke: an mRS score of <2 at 90 days or one that does not result in an increase in at least 1 mRS category from an individual's prestroke baseline

mRS, Modified Rankin Scale. *Patients with nonfocal global encephalopathy will not be reported as a stroke without unequivocal evidence of cerebral infarction-based upon neuroimaging studies (CT scan or Brain MRI). †Modified Rankin Scale assessments should be made by qualified individuals according to a certification process.²³⁻²⁵

TABLE 5. Bleeding

Life-threatening or disabling bleeding
Fatal bleeding (BARC type 5) OR
Bleeding in a critical organ, such as intracranial, intraspinal, intraocular, or pericardial necessitating pericardiocentesis, or intramuscular with compartment syndrome (BARC type 3b and 3c)
OR
Bleeding causing hypovolemic shock or severe hypotension requiring vasopressors or surgery (BARC type 3b) OR
Overt source of bleeding with drop in hemoglobin ≥ 5 g/dL or whole blood or packed red blood cells (RBCs) transfusion ≥ 4 units* (BARC type 3b)
Major bleeding (BARC type 3a)
Overt bleeding either associated with a drop in the hemoglobin level of at least 3.0 g/dL or requiring transfusion of 2 or 3 units of whole blood/RBC, or causing hospitalization or permanent injury, or requiring surgery AND
Does not meet criteria of life-threatening or disabling bleeding
Minor bleeding (BARC type 2 or 3a, depending on the severity)
Any bleeding worthy of clinical mention (eg, access site hematoma) that does not qualify as life-threatening, disabling, or major

BARC, Bleeding Academic Research Consortium²⁹; *RBC*, red blood cell. *Given that 1 unit of packed RBC typically will raise the hemoglobin concentration by 1 g/dL, an estimated decrease in hemoglobin will be calculated.

TABLE 6. Acute kidney injury (AKIN classification*)

Stage 1
Increase in serum creatinine to 150%-199% (1.5-1.99 \times increase compared with baseline) OR increase of ≥ 0.3 mg/dL (≥ 26.4 mmol/L) OR
Urine output <0.5 mL/kg/h for >6 but <12 h
Stage 2
Increase in serum creatinine to 200%-299% (2.0%-2.99% increase compared with baseline) OR
Urine output <0.5 mL/kg/h for >12 but <24 h
Stage 3†
Increase in serum creatinine to $\geq 300\%$ (>3 \times increase compared with baseline) OR serum creatinine of ≥ 4.0 mg/dL (≥ 354 mmol/L) with an acute increase of at least 0.5 mg/dL (44 mmol/L) OR
Urine output <0.3 mL/kg/h for ≥ 24 h OR
Anuria for ≥ 12 h

The increase in creatinine must occur within 48 h. *Mehta et al.³¹ †Patients receiving renal replacement therapy are considered to meet Stage 3 criteria irrespective of other criteria.

TABLE 7. Vascular access site and access-related complications

Major vascular complications
Any aortic dissection, aortic rupture, annulus rupture, left ventricle perforation, or new apical aneurysm/pseudoaneurysm OR
Access site or access-related vascular injury (dissection, stenosis, perforation, rupture, arterio-venous fistula, pseudoaneurysm, hematoma, irreversible nerve injury, compartment syndrome, percutaneous closure device failure) leading to death, life-threatening or major bleeding,* visceral ischemia, or neurological impairment OR
Distal embolization (noncerebral) from a vascular source requiring surgery or resulting in amputation or irreversible end-organ damage OR
The use of unplanned endovascular or surgical intervention associated with death, major bleeding, visceral ischemia or neurological impairment OR
Any new ipsilateral lower extremity ischemia documented by patient symptoms, physical exam, and/or decreased or absent blood flow on lower extremity angiogram OR
Surgery for access site-related nerve injury OR
Permanent access site-related nerve injury
Minor vascular complications
Access site or access-related vascular injury (dissection, stenosis, perforation, rupture, arterio-venous fistula, pseudoaneuysms, hematomas, percutaneous closure device failure) not leading to death, life-threatening or major bleeding,* visceral ischemia, or neurological impairment OR
Distal embolization treated with embolectomy and/or thrombectomy and not resulting in amputation or irreversible end-organ damage OR
Any unplanned endovascular stenting or unplanned surgical intervention not meeting the criteria for a major vascular complication OR
Vascular repair or the need for vascular repair (via surgery, ultrasound-guided compression, transcatheter embolization, or stent-graft)
Percutaneous closure device failure
Failure of a closure device to achieve hemostasis at the arteriotomy site leading to alternative treatment (other than manual compression or adjunctive endovascular ballooning)

*Refers to VARC bleeding definitions.

TABLE 8. Conduction disturbances and arrhythmias

Up to 72 h, continuous rhythm monitoring is recommended in order to maximize the detection of arrhythmias
Data elements to be collected should include
Baseline conduction abnormalities, paroxysmal or permanent atrial fibrillation (or flutter), and the presence of permanent pacemaker*
Implant-related new or worsened cardiac conduction disturbance (new or worsened first-degree atrioventricular (AV) block, second-degree AV block (Mobitz I or Mobitz II), third-degree AV block, incomplete right bundle branch block, right bundle branch block, intraventricular conduction delay, left bundle branch block, left anterior fascicular block, or left posterior fascicular block, including block requiring a permanent pacemaker implant
Persistent or transient high-degree AV block. High-grade AV block is persistent if it is present every time the underlying rhythm is checked
New permanent pacemaker implantation, with precision of the indication and the number of days postimplant of the placement of new permanent pacemaker
New-onset atrial fibrillation (or flutter)†
Any new arrhythmia resulting in hemodynamic instability or requiring therapy‡

*Type of permanent pacemaker should be recorded (eg, defibrillator, single vs dual chamber, biventricular). †New-onset atrial fibrillation (or flutter) is diagnosed as any arrhythmia within hospitalization that has the ECG characteristics of atrial fibrillation (or flutter) and lasts sufficiently long to be recorded on a 12-lead ECG, or at least 30 s on a rhythm strip. ‡Therapy includes electrical/medical cardioversion or initiation of a new medication (oral anticoagulation, rhythm, or rate controlling therapy).

TABLE 9. Other TAVI-related complications

Conversion to open surgery	Conversion to open sternotomy during the TAVI procedure secondary to any procedure-related complications
Unplanned use of cardiopulmonary bypass (CPB)	Unplanned use of CPB for hemodynamic support at any time during the TAVI procedure
Coronary obstruction	Angiographic or echocardiographic evidence of a new, partial or complete, obstruction of a coronary ostium, either by the valve prosthesis itself, the native leaflets, calcifications, or dissection, occurring during or after the TAVI procedure
Ventricular septal perforation	Angiographic or echocardiographic evidence of a new septal perforation during or after the TAVI procedure
Mitral valve apparatus damage or dysfunction	Angiographic or echocardiographic evidence of new damage (chordae papillae muscle, or to the leaflet) to the mitral valve apparatus or dysfunction (eg, restrictions due to the THV) of the mitral valve during or after the TAVI procedure
Cardiac tamponade	Evidence of a new pericardial effusion associated with hemodynamic instability and clearly related to the TAVI procedure
Endocarditis	
Any 1 of the following:
 
Fulfilment of the Duke endocarditis criteria*
 
Evidence of abscess, paravalvular leak, pus, or vegetation confirmed as secondary to infection by histological or bacteriological studies during a reoperation
 
Findings of abscess, pus, or vegetation involving a repaired or replaced valve during an autopsy

Valve thrombosis	Any thrombus attached to or near an implanted valve that occludes part of the blood flow path, interferes with valve function, or is sufficiently large to warrant treatment. Note that valve-associated thrombus identified at autopsy in a patient whose cause of death was not valve-related should not be reported as valve thrombosis
Valve malpositioning	
Valve migration
 
After initial correct positioning, the valve prosthesis moves upwards or downwards, within the aortic annulus from its initial position, with or without consequences

Valve embolization	The valve prosthesis moves during or after deployment such that it loses contact with the aortic annulus
Ectopic valve deployment	Permanent deployment of the valve prosthesis in a location other than the aortic root
TAV-in-TAV deployment	An additional valve prosthesis is implanted within a previously implanted prosthesis because of suboptimal device position and/or function, during or after the index procedure

TAVI, Transcatheter aortic valve implantation; THV, transcatheter heart valve.
*Durack et al.⁷²

TABLE 10. Prosthetic valve dysfunction

Prosthetic aortic valve stenosis*			
	Normal	Mild stenosis	Moderate/severe stenosis
Quantitative parameters (flow-dependent)†			
Peak velocity (m/s)	<3 m/s	3-4 m/s	>4 m/s
Mean gradient (mm Hg)	<20 mm Hg	20-40 mm Hg	>40 mm Hg
Quantitative parameters (flow-independent)			
Doppler velocity index‡	>0.35	0.35-0.25	<0.25
Effective orifice area§	>1.1 cm ²	1.1-0.8 cm ²	<0.8 cm ²
Effective orifice area	>0.9 cm ²	0.9-0.6 cm ²	<0.6 cm ²
Prosthesis-patient mismatch (PPM)			
	Insignificant	Moderate	Severe
Indexed effective orifice area¶ (cm ² /m ²)	>0.85 cm ² /m ²	0.85-0.65 cm ² /m ²	<0.65 cm ² /m ²
Indexed effective orifice area# (cm ² /m ²)	>0.70 cm ² /m ²	0.90-0.60 cm ² /m ²	<0.60 cm ² /m ²
Prosthetic aortic valve regurgitation			
	Mild	Moderate	Severe
Semiquantitative parameters			
Diastolic flow reversal in the descending aorta—PW	Absent or brief early diastolic	Intermediate	Prominent, holodiastolic
Circumferential extent of prosthetic valve paravalvular regurgitation (%)**	<10%	10%-29%	≥30%
Quantitative parameters‡			
Regurgitant volume (mL/beat)	<30 mL	30-59 mL	≥60 mL
Regurgitant fraction (%)	<30%	30-49%	≥50%
EROA (cm ²)	0.10 cm ²	0.10-0.29 cm ²	≥0.30 cm ²

PW, Pulsed wave; EROA, effective regurgitant orifice area. *In conditions of normal or near normal stroke volume (50-70 mL). †These parameters are more affected by flow, including concomitant aortic regurgitation. ‡For LVOT >2.5 cm, significant stenosis criteria is <0.20. §Use in setting of BSA ≥1.6 cm² (note: dependent on the size of the valve and the size of the native annulus). ||Use in setting of BSA <1.6 cm². ¶Use in setting of BMI <30 kg/cm². #Use in setting of BMI ≥30 kg/cm². **Not well-validated and may overestimate the severity compared with the quantitative Doppler.

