During the entire study period, adverse events will be closely monitored by the trial PI and clinical trial coordinator of this study, working along with the study DSMB. In particular, formal stopping rules on the 6-month mortality are stipulated in this protocol (please refer to section 4.1 “Efforts to minimize procedure risks”). In addition, in the event that other adverse events (e.g., surgical complications) are thought to be excessive for the study patient population at any point of the trial, the patient accrual to the trial will be suspended immediately, pending a review of all adverse events data. A final decision will be made by the trial PI and DSMB as to whether the trial should be amended, terminated or continue accrual. Such decision should be filed with and pre-approved by the institutional IRB.

2.4 Study Endpoints:

The primary safety endpoint is procedural success at 30-days. Procedural success will include:

- Successful vascular access without unplanned major vascular complication as defined by VARC-2, delivery and retrieval of the transcatheter valve delivery system, correct position of both the vascular stent(s) and transcatheter valve in the IVC, a single valve placed within the IVC, and no need for additional surgery or re-intervention (including drainage of pericardial effusion) with the patient being alive at 30-days.

The primary efficacy endpoint will be improvement in one of three variables assessed from baseline to 6-months.

- Improvement of KCCQ score >15. This has been shown to correlate with improvement in quality of life with heart failure patients²².
- Improvement in 6-minute walk test (6MWT)>70 meters. This has been shown to provide prognostic information in patients with congestive heart failure after an intervention²³.
- Improvement of greater than 6% of peak Vo2 in cardiopulmonary exercise testing. In a heart failure population, this has been shown to help assess prognosis in patients who were instituted in an exercise program ²⁴.

Secondary endpoints will be evaluated at several timepoints and will be divided into safety and efficacy: The first in the acute setting which will be out to 30 days or hospital discharge whichever being longer; additional time points will be at midterm (6 months post-procedure), long term (1 year and annually up to 5-years post-procedurally.)

Secondary safety endpoints include:

- All stroke and TIA (VARC-2)
- Mortality (VARC-2)
- Myocardial infarction (VARC-2)

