- Acute Kidney Injury (VARC-2)
- Major Vascular Complication (VARC-2)

Secondary efficacy endpoints include:

- Assessment of improvement of LE edema by the Villalta Score²⁵. A 3.1 point improvement in this scale was associated with improved quality of life²⁶.

Besides the above formal secondary endpoints, we will monitor for the following throughout the trial:

- Deep Vein/IVC thrombosis or pulmonary embolism
- Improvement in grades of tricuspid regurgitation as assessed by echocardiogram
- Changes in TAPSE by echocardiogram for RV function
- Pleural effusions
- Additional quality questionnaires to assess for changes in ascites (EORTC QLQ-C30²⁷ and ESAS-AM²⁸). A 10-point change in mean score in the QLQ-C30 has been shown to be a meaningful response (O'Connor R. Measuring Quality of Life in Health Churchill Livingstone: Philadelphia; 2004). A decrease of 1.25 points in the ESAS-AM has been shown to correlate with symptom improvement after paracentesis²⁸.

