5.1 Pre-Procedure Assessments

The following will be collected in all patients at baseline (within 90 days of procedure, except for Informed Consent which will be obtained prior to beginning screening). Items in bold font are required to determine eligibility and must be performed prior to the Heart Team and Executive Committee meetings.

- **Informed Consent**
- **Medical history.** This will include past medical and surgical history, social history, family history.
- **Physical Exam.** This will include vital signs and weight, head, ears, eyes, nose and throat (HEENT), neck, lungs, cardiovascular, abdomen, genitourinary, gastrointestinal, musculoskeletal, neurological
- **NYHA functional Class** as per The Criteria Committee of the New York Heart Association. *Nomenclature and Criteria for Diagnosis of Diseases of the Heart and Great Vessels*. 9th ed. Boston, Mass: Little, Brown & Co; 1994:253-256
- **Diuretic types and doses**
- Surgical note documenting high risk/inoperable status.

Laboratory Measurements

- CBC with differential (During 6 months of screening and within 21 days of procedure)
- Cardiac Enzymes (Troponin I and/or CK and CKMB) (≤ 72 hours before the procedure)
- **Comprehensive metabolic panel** (within 90 days of procedure)
- Lactate Dehydrogenase (LDH)
- ACT (within 21 days of procedure)
- aPTT (within 21 days of procedure)
- **PT/INR** (within 90 days of procedure)
- Brain Natriuretic Peptide (BNP) (within 21 days of procedure)

Non-Invasive Tests

- ECG (within 21 days of procedure)
- Chest X-ray (portable or PA and lateral) (within 21 days of procedure)
- **Echocardiogram** (Transthoracic) (within 90 days of procedure)
- **Chest and Abdominal CT** (within 90 days of procedure)
- Cardiopulmonary Exercise Stress test ³² (within 90 days of procedure)
- Venous Lower Extremity Duplex Study (within 21 days of procedure)
- **Pulmonary Function Testing** (PFT) (within 90 days of procedure)

Functional Assessments

- 6-minute walk test ³³ (within 90 days of procedure)
- Villalta Scale ^{25,26} (within 21 days of procedure)
- EORTC QLQ-C30 ²⁷ (within 21 days of procedure)
- ESAS-AM ²⁸ (within 21 days of procedure)
- Kansas City Cardiomyopathy Questionnaire (KCCQ) ²² (within 21 days of procedure)

Invasive Tests

- **Left Heart Catheterization with or without LV gram and IVUS.** (Within one year of baseline)
- **Right Heart Catheterization** (within 90 days of procedure)

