Acute evaluation - When the SRDL has been exceeded, clinical follow-up essential for early detection and management of skin injuries. The patient should be advised of the possibility of a skin injury due to a tissue reaction, and should be told to examine the beam entrance site at 2-4 weeks after the procedure. The operator should be notified if any skin changes are seen. Patients who have not previously notified the operator should be contacted by telephone at approximately 30 days after the procedure, in order to ensure that a skin injury is not missed.

Long-term evaluation - If a skin injury is suspected, the interventionalist should see the patient at an office visit, and should arrange for appropriate follow-up care. The physician responsible for the patient's care should be informed of the possibility of radiation effects.

5.3 Post-Procedure assessments:

Study patients will be continuously monitored clinically, hemodynamically, and electrocardiographically during catheterization for all local, systemic side effects and complications. After completion of the procedure, patients will be admitted to the hospital for further monitoring.

- Physical Exam. This will include vital signs and weight, head, ears, eyes, nose and throat (HEENT), neck, lungs, cardiovascular, abdomen, genitourinary, gastrointestinal, musculoskeletal, neurological
- NYHA functional Class as per The Criteria Committee of the New York Heart Association. *Nomenclature and Criteria for Diagnosis of Diseases of the Heart and Great Vessels*. 9th ed. Boston, Mass: Little, Brown & Co; 1994:253-256
- Diuretic types and doses
- Event assessment as per VARC-2¹⁹.

Laboratory Measurements

- CBC with differential
- Cardiac Enzymes (Troponin I and/or CK and CKMB) every 8 hours x3
- Comprehensive metabolic panel
- Lactate Dehydrogenase (LDH)
- ACT (optional)
- PT/INR
- Brain Natriuretic Peptide (BNP)

Non-Invasive Tests

- ECG
- Echocardiogram (Transthoracic)

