5.6 Annual Study Visit, Final Study Visit, premature discontinuation or unscheduled study visit

The following variables will be collected for the above parameters.

- Physical Exam. This will include vital signs and weight, head, ears, eyes, nose and throat (HEENT), neck, lungs, cardiovascular, abdomen, genitourinary, gastrointestinal, musculoskeletal, neurological
- NYHA functional Class as per The Criteria Committee of the New York Heart Association. *Nomenclature and Criteria for Diagnosis of Diseases of the Heart and Great Vessels*. 9th ed. Boston, Mass: Little, Brown & Co; 1994:253-256
- Diuretic types and doses
- Event assessment as per VARC-2 ¹⁹.

Table 1: Summary Schedule of Procedure and Follow-Up

	Baseline	During the procedure	24 hrs. after the procedure	7 days after procedure or at discharge	At 30 days (+/- 7 days)	At 6 months (+/- 14 days)	At 1 yr (+/- 21 days)	Annually up to 5 years (+/- 21 day)	Premature discontinuation or unscheduled visit
Informed Consent	Xb†								
Medical History	Xb†								
Physical Exam (incl. Vital signs)	Xb†		X	X	X	X	X	X	X
NYHA Class	Xb†		X	X	X	X	X	X	X
Diuretic types and doses	Xb†		X	X	X	X	X	X	X
Event Assessment	Xb		X	X	X	X	X	X	X
Surgical note documenting high risk/inoperable status	Xb†								

Laboratory Measurements								
CBC with Differential	Xd		x	X		X	X	
Cardiac Enzymes (Troponin I and/or CK and CK-MB)	Xe		X (every 8 hours x 3)					
Comprehensive Metabolic Panel	Xb†		X	X	X	X	X	
LDH (to assess hemolysis)	Xc		X	X	X	X	X	
ACT^		X*	X*					
aPTT	Xc	X*						
PT/ INR	Xb†		X					
Brain Natriuretic Peptide (BNP)	Xc		x	X	X	X	X	
Haptoglobin	Xc			X	X	X	X	
Non-Invasive Tests								
ECG	Xc		X		X	X	X	
Chest X-ray	Xc				X	X	X	
Echocardiogram - TTE or TEE	Xb†	X	X		X	X	X	
Chest and/or Abdominal CT	Xa†					X		
Cardiopulmonary Exercise Stress test	Xb					X		
Venous Lower Extremity Duplex Study	Xc							
Pulmonary Function Test (PFT)	Xb†							
Functional Assessments								
6-Minute Walk Test	Xb				X	X	X	
Quality of Life (Kansas City Cardiomyopathy Questionnaire (KCCQ))	Xc				X	X	X	
Villalta Scale	Xc				X	X	X	
EORTC QLQ-C30	Xc				X	X	X	
ESAS-AM	Xc				X	X	X	
Invasive Tests								
Left Heart Catheterization w/wo LV gram and IVUS ^a	Xa†	X*						
Right Heart Catheterization	Xb†	X				X		

- a. The following assessment will be collected within one year of procedure day.
- b. The following assessments will be completed within 90 days before the procedure day

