- c. The following assessments will be completed within 21 days before the procedure.
- d. The following assessment needs to be done during the 6 months screening and within 21 days before the procedure.
- e. CK/CKMB and/or Troponins ≤ 72 hours before the procedure
- f. Right heart catheterization only

* Optional

† Required prior to Heart Team and Executive Committee meetings to determine eligibility

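### The scheduled creatinine samples do not ensure a valid 48 h comparison for the acute kidney injury endpoint

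*Combined protocol and SAP*

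**What the plan says.** Section 2.4 lists "Acute Kidney Injury (VARC-2") among the secondary safety endpoints. It sets the first assessment period as follows: "The first in the acute setting which will be out to 30 days or hospital discharge whichever being longer".

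Appendix B Table 6 gives the definition. For Stage 1 the creatinine criterion is a 1.5-fold to 1.99-fold "increase compared with baseline) OR increase of ≥ 0.3 mg/dL". The table note adds: "The increase in creatinine must occur within 48 h". Low urine output is an alternative criterion at every stage, and renal replacement therapy counts as Stage 3 by itself.

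The sampling is in Sections 5.1, 5.3, 5.4 and 5.5 and in Table 1. Before the procedure, Section 5.1 asks for a "Comprehensive metabolic panel (within 90 days of procedure"). Table 1 codes this panel with footnote b ("The following assessments will be completed within 90 days before the procedure day") and with the dagger ("Required prior to Heart Team and Executive Committee meetings to determine eligibility"). After the procedure, Table 1 places a panel at 24 h, at day 7 or discharge, at 30 days, at 6 months and at 1 year. Nothing is marked in the column for the procedure itself. Urine output appears neither in Table 1 nor in Sections 5.1 to 5.6.

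**The concern.** A definition with a 48 h limit needs a recent pre-procedure value and a second value soon enough after it. The schedule assures neither. The baseline panel belongs to the eligibility work-up, and the first two post-procedure panels may be six days apart.

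The myocardial infarction endpoint is better served. Its enzymes are drawn no more than 72 h before the procedure and then serially: "Cardiac Enzymes (Troponin I and/or CK and CKMB) every 8 hours x3". The metabolic panel has no such provision.

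Renal outcome matters in this trial. Section 2.1 rests the rationale partly on protecting the renal veins, Section 4.2 lists better kidney function as a possible benefit, and Section 4.0 lists renal failure as a risk. The procedure in Section 5.2.1 includes two cavograms and a right ventricular angiogram. If the AKI count depends on when blood happened to be drawn, the trial's description of acute renal safety is weakened.

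**Working it through.** The documents give no planned AKI rate or precision to reproduce, so the check compares sampling intervals with the 48 h limit. It assumes that creatinine is part of the metabolic panel, whose components are not listed.

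**Inputs**
- Limit: 48 h, starting point not stated (Appendix B Table 6).
- Baseline panel: L days before the procedure, L up to 90 (Section 5.1; Table 1 footnote b).
- Post-procedure panels: 24 h, then day 7 or discharge on day D (Table 1).
- Up to 15 patients (Section 2.3).

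**Reading A: the 48 h is the interval between two creatinine values**

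Baseline to the 24 h sample: interval = 24 × L + 24 hours.
- L = 1: 48 h, qualifies.
- L = 2: 72 h, fails.
- L = 7: 192 h, fails.
- L = 90: 2,184 h, fails.

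The pre-procedure value therefore qualifies only when drawn within 24 h before the procedure. The distribution of L is not given. As an illustration only, if L were spread evenly over W days, the qualifying share is 1/W: 14.3% for W = 7, 3.3% for W = 30 and 1.1% for W = 90. In practice such short leads are unlikely. The panel must precede a weekly heart team conference (Section 2.2.1) and the executive committee's review, and the implantation date is set only after that committee agrees (Section 2.2.3).

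24 h sample to the next sample: interval = 24 × D − 24 hours.
- D = 2: 24 h, qualifies.
- D = 3: 48 h, qualifies.
- D = 4: 72 h, fails.
- Day 7: 144 h, fails.

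This pair works only if discharge is by about day 3. Its reference is then a post-procedure value, so it cannot see a rise that has already happened by 24 h. The 30-day and later panels cannot form a 48 h pair.

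**Reading B: the 48 h runs from the procedure**

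The 24 h sample lies inside the window and can be compared with baseline. That comparison can span 90 + 1 = 91 days, so change before the procedure can count as AKI. Contrast CT is also part of the pre-meeting work-up (Section 5.1; Appendix C), and its order relative to the panel is not fixed, so the reference may predate a separate contrast exposure. The discharge sample falls inside the window only if discharge is by day 2 (24 × 2 = 48 h). Otherwise a peak after 24 h can be missed.

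**Size per case**

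1/15 = 6.7 percentage points of the AKI rate for each misclassified patient. The number misclassified would need the baseline lead times, the lengths of stay, the variability of creatinine and the timing of injury. None of these is in the documents.

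**The case against.** The strongest reply is that the endpoint still works. The table note does not say that the 48 h separates two samples. Counted from the procedure, the 24 h panel is in time and the protocol's own baseline is the comparator. Discharge on day 2 or 3 gives a qualifying pair even on the stricter reading. Renal replacement therapy qualifies without any creatinine. Patients are admitted for monitoring with VARC-2 event assessment (Sections 5.3 and 5.4), and nothing bars an assessor from using unscheduled inpatient creatinine or charted urine output. AKI is also one of five secondary safety endpoints, reported descriptively. If 3 of 15 patients had AKI, an assumed count for illustration, the exact 95% interval would be 4.3% to 48.1%, so one or two wrong classifications sit inside existing imprecision.

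Much of this stands. A reader might infer that the definition usually cannot be applied. The documents do not support that: it depends on one of two possible readings and on a length of stay that is not given. Nor do they support the claim that the AKI rate says nothing about renal harm, or any count of patients misclassified.

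The reply does not remove the gap. Under either reading the scheduled samples leave the comparison unsecured. Unscheduled values may exist, but nothing requires them, so case finding would vary by site and patient. Wide intervals describe sampling error; they do not correct a stale reference or a missed peak.

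**Conclusion.** The concern holds in a limited form: the schedule does not ensure a valid 48 h creatinine comparison, and the protocol names neither the AKI reference value nor the start of the window. With an interval between values, the pre-procedure sample qualifies only at a lead of 24 h or less, and the 24 h and discharge pair only with discharge by about day 3. With a window from the procedure, the criterion is usable but open to drift since baseline and to missed later peaks.

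The effect is 6.7 percentage points per misclassified case at 15 patients, with an unknown number of cases. It rests on creatinine being part of the metabolic panel. It touches one descriptive secondary safety endpoint and neither the primary endpoints in Section 2.4 nor the stopping rules in Section 4.1.3. It is a cheap improvement rather than a flaw that threatens the trial's main conclusions.

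**What to change.** - In Sections 5.1 and 5.3 and in Table 1, add a creatinine on the day of the procedure, before contrast, as the AKI reference. Keep the 24 h sample, and add one at 48 h, or at discharge if that is earlier.
- In Section 2.4, state that AKI by Appendix B Table 6 is an acute-phase endpoint, measured against that reference, with the 48 h counted from the procedure. The starting point needs stating because a reference drawn shortly before the procedure lies slightly more than 48 h before the 48 h sample.
- Report renal function at later visits as change in creatinine.

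The cost is up to two extra creatinine results per patient, 2 × 15 = 30 in all, and a small amendment. The 48 h sample needs a new blood draw, because three enzyme draws at 8 h spacing end at about 24 h. The change should be made before patients are treated, since a missing pre-procedure value cannot be recovered afterwards.
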